13.0 STATISTICAL CONSIDERATIONS

- 13.1 The proposed pilot Phase III randomized controlled clinical trial aims to determine which of the following treatments is superior in arresting dental caries among patients presenting with interproximal caries scoring RA1 RA3 on the International Caries Classification and Management System (ICCMS): (1) Fluoride varnish (FV, current standard of care, control), (2) Super floss + SDF + FV, (3) SDF + FV. We hypothesize that group 2 will have the best outcomes, as measured by no change or reversal in ICCMS classification indicating no caries progression or remineralization on radiographic examination, (higher score indicates progression) followed by group 3. As we could find no data on ICCMS-defined progression or remineralization rates for either Super Floss or fluoride, we were unable to calculate power. Instead, we provide estimates of recruitment based on feasibility. We expect to accrue approximately 20 participants, with 2 qualifying teeth per participant, in each group.
- 10% loss to follow up has increased dramatically to ~48%. Given this unexpected setback, we now need to continue recruiting participants to reach sufficient power. We originally planned to enroll 39 subjects in the study, but would now like to add 21 new participants for a total of 60 participants.

Descriptive statistics will be calculated for all demographic and clinical characteristics to assess the degree to which randomization was successful using means and standard deviations or medians and interquartile ranges for continuous variables and counts and percentages for categorical variables.

The primary analysis will be by intent-to-treat. The primary outcome is the change in ICCMS category, as assessed by radiographic evidence, from baseline to 12 months, with a planned interim analysis to evaluate the endpoint at 6 months for early indications of efficacy. We will calculate the median difference at each time point and use an individual-level model with an adjustment to the standard error to account for the clustering. First we will evaluate the association between treatment groups and the change in ICCMS score from baseline at 6 and 12 months using a cluster-adjusted chi-squared test. We will further assess

14

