the relationship between these two variables using generalized estimating equations, specifying a Poisson (or negative binomial, if overdispersed) family and a log link. We will also specify an exchangeable correlation matrix and a robust standard error.

Since the study is randomized, we do not anticipate needing to adjust for any confounders. However, should we find any differences in demographic or clinical variables at baseline, we will investigate them as potential confounders, which will be defined as those variables which alter the odds ratio by >15% when included in the model.

For those with missing data on outcomes or other covariates to be included in the model, we will consider multiple imputation methods if the amount of missing data is <10%. To assess the impact of missing data, we will compare those with missing data to those not missing data with respect to demographic and clinical variables to assess comparability. Should imputation be utilized, a sensitivity analysis will be conducted excluding those for whom data was imputed to assess the impact of imputation.

Model fit will be evaluated by inspection of residuals and influential points. As we are conducting an interim analysis, we will use a two-sided Bonferroni-corrected p-value of a=.025 for statistical significance. Finally, to assess the degree to which the two raters agree with respect to classifying the outcome of the x-rays, we will calculate and report Kappa. All statistical analyses will be done using Stata 15.0 (College Station, TX).

Power Analysis

We calculated power using a cluster-randomized design. We were unable to locate any previous studies examining the impact of these three treatments (or any two) using the same classification system as our outcome. However, we were able to obtain an estimate of 0.0 to 0.25 for the interclass correlation coefficient (ICC) (Honkala et al., 2011). Assuming the mean ICC, and assuming a clinically significant mean difference of 0.2, a standard deviation of 0.2, a covariance of cluster sizes of 0.65, two caries on average per child, and a two-sided adjusted Type I error rate of 0.025 to account for the three time points at which the data will be analyzed, we will have 80% power with 11-12 participants per group, for a total of 33-36 participants (66-72 caries). Since we anticipate significant loss-to-follow-up over the course

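### With about 10 children per arm, the uncorrected robust standard error does not hold the 2.5% level if the ICCMS change score is analysed; the size of the error depends on how the outcome is coded

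*Combined protocol and SAP*

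**What the plan says.** Section 13.1 defines the outcome for analysis: "The primary outcome is the change in ICCMS category, as assessed by radiographic evidence, from baseline to 12 months". A cluster-adjusted chi-squared test comes first. A GEE model then follows, "specifying a Poisson (or negative binomial, if overdispersed) family and a log link", and the plan adds: "We will also specify an exchangeable correlation matrix and a robust standard error". On the significance level: "we will use a two-sided Bonferroni-corrected p-value of a=.025 for statistical significance". Nothing in section 13 names a small-sample variance, a t or F reference distribution, or a randomisation test.

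On numbers, section 13.1 reports that "10% loss to follow up has increased dramatically to ~48"%, and it raises the total to 60. The Power Analysis says "we will have 80% power with 11-12 participants per group, for a total of 33-36 participants (66-72 caries"). Section 6.3 randomises children 1:1:1 in blocks of six, and section 3.5 discards the data of those who drop out.

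**The concern.** The robust (sandwich) variance is justified when there are many independent clusters. With few clusters it is biased downwards, and a normal or chi-squared reference ignores its own sampling error. Both faults make p-values too small and intervals too narrow. The clusters here are children, and few will remain. If the test rejects more often than 2.5% when there is no effect, the threshold the plan sets is not the one it applies, and a claim that one treatment is superior rests on weaker evidence than stated.

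**Working it through.** **1. The plan's own figure.** The inputs are in the Power Analysis: "a standard deviation of 0.2, a covariance of cluster sizes of 0.65, two caries on average per child" (0.65 read as the coefficient of variation, CV), a target difference of 0.2 between arm means, a mean intracluster correlation of 0.125 (midpoint of 0.0 to 0.25), two-sided 0.025 and 80% power.
- Lesions per arm before clustering: 2 × (2.2414 + 0.8416)² × (0.2/0.2)² = 19.01.
- Design effect: 1 + ((0.65² + 1) × 2 − 1) × 0.125 = 1.2306.
- Lesions per arm: 19.01 × 1.2306 = 23.4. Children per arm: 23.4 / 2 = 11.7.

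This reproduces the stated 11–12.

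**2. Children left.** 60 × 0.52 / 3 = 10.4 per arm. If 54 are recruited, 54 × 0.52 / 3 = 9.4.

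**3. A case needing no simulation.** Take equal lesion numbers per child, a mean-difference scale and roughly normal child means. The robust variance is then (n − 1)/n times the unbiased one, so the true error is P(|t with 2n − 2 df| > 2.2414 × √((n − 1)/n)).

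| Children per arm | True error at nominal 2.5% |
|---|---|
| 9 | 5.1% |
| 10 | 4.8% |
| 12 | 4.3% |
| 20 | 3.5% |

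Reaching the planned 12 per arm therefore still leaves 4.3 / 2.5 = 1.7 times the nominal rate.

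**4. Simulated null trials**, about 10 children per arm, nominal 2.5%. The documents give no distribution for the change score, so one was assumed (for example 20% improve, 55% unchanged, 25% progress; or −1/0/1/2 with probabilities 0.10/0.60/0.25/0.05). Lesions average two per child.

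| Coding and scale | Lesions per child | Pairwise | Joint three-arm |
|---|---|---|---|
| Signed change, mean difference | equal | 4.5–4.9% | 6.4–6.7% |
| Signed change, mean difference, separate simulations | unequal in those that state it | 4.2–5.6% | 6.3–7.0% |
| Signed change, mean difference | CV 0.65 | 5.8–6.1% if the working correlation is held at or above 0; otherwise 7.2–7.7% | 8.4–11.4% |
| Change shifted to be non-negative, log link | equal | 3.8–4.0% | 5.3% |
| Change shifted to be non-negative, log link | CV 0.65 | 4.8–6.4% | 6.9–9.7% |
| Binary arrest, log link | unequal | 2.4–3.1% | 3.6–5.0% |
| Binary progression at 20–30%, log link | equal or unequal | 1.0–3.0% | 1.4–4.6% |

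A further run of the shifted score gave 4.5% pairwise and 6.4% joint. Multiplying the variance by M/(M − 1), with M the number of children, helps little: signed-change pairwise error is still 4.2–4.6% with equal numbers and 6.8–7.3% at CV 0.65.

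The favourable binary results are not uniform. With 40% progression, unequal lesion numbers and random loss, one run gave 4.7% pairwise. Progression steps scored 0/1/2 gave 1.2–3.0% in some runs, but up to 5.5% when 45% of lesions progressed.

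**5. Candidate remedies.**
- Mancl-DeRouen variance with a t reference: pairwise error 1.8–2.8% on the change score, but only 0.2–1.0% in most binary and progression-step log-link runs. Its joint F test at CV 0.65 still gave 3.5–4.3%.
- Child-level permutation: 1.7–2.7% across the signed score and progression steps, and 2.3% on binary progression. In one set of trials where the robust test gave 5.6%, permutation gave 1.9%.
- Permuting only completers within blocks of six: with ten blocks and 48% random loss, about 24% of children in a two-arm comparison have no comparator left in their block. The median number of distinct arrangements is 432. In about 5% of draws there are 24 or fewer, and p cannot then fall below 1/24 = 4.2%.

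**The case against.** The strongest objection is that the inflated rates do not belong to the model as written. A Poisson model with a log link cannot take a signed change score, because some values are negative. The mean-difference results describe a substituted scale, and the shift to non-negative values is a recoding the plan does not mention. Section 10.0 describes the outcome as arrest, and on that coding the pairwise test is close to 2.5%. This stands, and it limits the point: until coding and scale are settled, the size of the error is not determined. It does not remove the point, because section 13.1 names change in category as the outcome and both workable ways of analysing that change give inflation.

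Three further objections stand in part. GEE is the second analysis, after the cluster-adjusted chi-squared test; no error rate was computed for that test, though no small-sample provision is stated for it either. The joint test is not specified for the GEE model. Section 12.0 calls the study small and preliminary, which lowers the stakes but does not change the level that the plan claims.

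A reader might infer that the false-positive rate is two to nearly three times the stated level whatever analysis is run, or that one corrected variance cures it everywhere. The documents support neither. At moderate settings the pairwise excess is about 1.7 to 2.2 times. Values near three come from the joint test, or from runs at CV 0.65 with the working correlation unrestricted. Mancl-DeRouen with t overcorrects for most log-link binary codings.

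**Conclusion.** The point holds for the change score. With about 10 children per arm, a nominal 2.5% pairwise test has a true error of about 4 to 5.5%, higher in some simulations at the plan's cluster-size variation. A joint test has about 6 to 7% or more (5.3% in the mildest shifted-score case). For binary arrest or progression with the log link, the pairwise test is near or below nominal in most runs. The rates are per look and per comparison. They rest on assumed change-score and cluster-size distributions and, at CV 0.65, on how a negative working correlation is handled. The direction for the change score does not rest on those assumptions alone: the equal-size calculation gives 4.8% at 10 per arm. The change is worth making before analysis.

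**What to change.** - **State the coding and scale first**, since the signed change cannot be fitted with the stated model and the interval method depends on the choice.
- **Primary p-value:** use a permutation test with the child as the unit. Re-run the blocked allocation over all randomised children and recompute the statistic in those analysed. This needs the envelope sequence and study numbers, not the discarded clinical data. Unrestricted permutation among children is an acceptable approximation. Do not permute only completers within blocks of six.
- **Chi-squared test:** obtain its p-value in the same way.
- **Intervals:** for a mean-difference or shifted change score, use a small-sample-corrected variance with a t reference. For a binary or progression-step log-link analysis, invert the permutation test.

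The cost is SAP wording, a little more code, somewhat wider intervals and some loss of nominal power; the loss was not quantified. No new visits or data are needed. Permutation restores the error rate under no treatment effect. It does not repair bias if loss to follow-up differs between arms.

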5.0 SELECTION AND WITHDRAWAL OF SUBJECTS

- 5.1 Inclusion Criteria:
 - 5.1.1 ASA I and ASA II children, aged 3-12, with interproximal decay on deciduous molars identified by radiographs. These teeth will not have previous restorations.
 - 5.1.2 Radiographic decay within enamel or extending to the dentin-enamel junction based on International Caries Classification and Management System (ICCMS)¹⁸ Categories 1 through 3 see above. Categories 1, 2 and 3 signify the extent of the "Initial Stages" of an interproximal carious lesion with radiolucency in the outer 1/2 of enamel, inner 1/2 of enamel, and outer 1/3 of dentin respectively.
 - 5.1.3 Interproximal lesions present without existing restorations, recurrent decay, or adjacent teeth with existing restorations.
 - 5.1.4 Behavior of the children should be within a Frankl 3 or 4 category²¹, indicating a "Positive" and "Definitely Positive" behavior rating, which would allow for safe and controlled execution of the proposed protocol.
- 5.2 Exclusion Criteria:
 - 5.2.1 Children who are not ASA I or ASA II.

- 5.2.2 Children who are allergic to or intolerant of SDF
- 5.2.3 Children who have known sensitivity to silver or heavy metal-ions, or have abnormal skin sensitization.
- 5.2.4 Children who have ulcerative gingivitis or stomatitis.
- 5.2.5 Carious interproximal lesions on primary molars in ICCMS Category 4, 5, or 6¹⁸, which signify the extent of the carious lesion radiographically reaching the middle 1/3 of dentin, inner 1/3 of dentin, and into the pulp respectively.
- 5.2.6 Behavior of a child within the Frankl 1 or 2 category²¹, indicating a "Definitely Negative" and "Negative" behavior, which may compromise safe application of SDF.
- 5.3 Withdrawal Criteria
 - 5.3.1 Patients can withdrawal voluntarily at any time.
 - 5.3.2 Any tooth which has progression of caries beyond ICCMS Category 3 will be withdrawn from the study. These teeth will be treated with appropriate restorative dental treatment according to the standard of care.
 - 5.3.3 Any qualifying tooth that subsequently requires a restoration or extraction due to trauma or exfoliates prematurely will be withdrawn from the study.
 - 5.3.4 Any study tooth whose adjacent tooth exfoliates before the end of this study and exposes the interproximal contact will be withdrawn from the study.

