6.0 STRATIFICATION/DESCRIPTIVE FACTORS/RANDOMIZATION SCHEME

- 6.1 We have not defined any *a priori* stratification factors.
- 6.2 Descriptive factors: Age, Gender, Race,, Date of Initial exam, Date of Recall exam/Followup, , Number of posterior caries on primary teeth that qualify for this present study, DMFS, Which interproximal surface (mesial or distal), Which primary molar, and Radiographic depth of Lesion based on ICCMS Categories (see Table 1 in Appendix).
- 6.3 Once participants have met eligibility criteria and have undergone the informed consent process (parental permission and assent, if applicable), they will be randomized to one of the three treatments 1:1:1 using a cluster-randomized design. That is, participants, not teeth, will be randomized, though multiple teeth per participant may be treated. Using the uniform distribution, the statistician will generate a random number sequence. We will use blocked randomization (blocks of six) to better ensure an even distribution across groups. Once group

Version date: 07/31/22

assignments have been made, the statistician will prepare numbered, opaque envelopes containing the random study arm assignments, which the investigators will use sequentially, as study participants accrue (i.e., the study identification number will match the number on the envelope).

7.0 STUDY AGENT ADMINISTRATION OR INTERVENTION AND TOXICITY MANAGEMENT PLAN

- 7.1 Treatment protocol after patients are randomized into one of three treatment groups:
 - 7.1.1 Fluoride varnish application (Control Group 1): Bulk saliva removed with saliva ejector. All teeth wiped dry with cotton gauze. One unit dose (0.4 ml) of fluoride varnish will be applied to all dentition then interproximal surfaces of all teeth will be flossed.
 - Professionally applied fluoride varnish has been shown to inhibit demineralization and enhance remineralization in early enamel caries.²² Current Caries Risk Assessment (CRA) protocol indicates fluoride varnish applications at 3-6 months intervals for high caries risk patients.^{4,5}

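### GEE covariates are to be picked by observed imbalance and a 15% shift in an odds ratio the model does not estimate; baseline ICCMS category should be prespecified instead

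*Combined protocol and SAP*

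**What the plan says.** Section 13.0 sets an unadjusted default: "Since the study is randomized, we do not anticipate needing to adjust for any confounders". It then makes an exception: "should we find any differences in demographic or clinical variables at baseline, we will investigate them as potential confounders". A confounder is defined as one of "those variables which alter the odds ratio by >15% when included in the model".

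The outcome is stated as follows: "The primary outcome is the change in ICCMS category, as assessed by radiographic evidence, from baseline to 12 months". The association with treatment is examined first "using a cluster-adjusted chi-squared test", and then further by generalized estimating equations, "specifying a Poisson (or negative binomial, if overdispersed) family and a log link", with an exchangeable correlation and robust standard errors.

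Section 6.2 lists "Radiographic depth of Lesion based on ICCMS Categories" among the descriptive factors. Lesions enter in categories 1 to 3 (section 5.1.2). There is no stratification (sections 6.1 and 14.1), so the design does not balance baseline depth.

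**The concern.** Three things are wrong with the covariate rule.

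- **It is not defined.** No size or test is given for a baseline difference. The criterion is an odds ratio, which the planned model does not produce. Three arms give several treatment ratios, and none is named. Two analysts could follow the text and fit different GEEs.
- **It is driven by the result.** A change-in-estimate rule admits a variable because it moves the treatment effect. In a randomised trial this small, chance imbalance supplies candidates.
- **It leaves the natural covariate to chance.** The outcome is change from baseline category, so the baseline value is part of the outcome. It is already recorded, yet it enters the GEE only if it trips the rule.

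At stake are a GEE whose form is fixed only after the data are seen, a possible modest rise in its type I error, and precision given up from a variable already in hand.

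**Working it through.** **1. The plan's own sample size contains no covariate.** Inputs from the power analysis in section 13.0: difference 0.2, SD 0.2, two-sided alpha 0.025, power 80%, two lesions per child, cluster-size variation 0.65 (read as a coefficient of variation), and the mean of ICC 0.0 to 0.25, taken as 0.125.

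- Lesions per arm: 2 × [0.2 × (z(0.9875) + z(0.80)) / 0.2]² = 19.01
- Design effect: 1 + [(0.65² + 1) × 2 − 1] × 0.125 = 1.2306
- Children per arm: 19.01 × 1.2306 / 2 = 11.70

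This reproduces the stated 11-12 per group without any covariate term.

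**2. Children likely to be analysed.** 60 × (1 − 0.48) = 31.2, or about 10 per arm.

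**3. The odds ratio and the model's ratio are different scales.** For a binary progression outcome with a ratio of 0.5 and assumed control risks of 10%, 30% and 50%, the odds ratio is 0.47, 0.41 and 0.33. For example, at 30%: (0.15/0.85) / (0.30/0.70) = 0.41. A 15% threshold on one scale is not the same rule on the other. The chi-squared test and the median differences involve no covariate-adjusted odds ratio either.

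**4. Type I error if the rule is read as a rate-ratio rule.** Two count-model simulations under the null, nominal 2.5%, eight baseline factors, baseline log-slope 0.4 per category. Progression rates and slope are assumptions, not figures from the documents. Simulation A: three arms, two lesions per child, only depth prognostic, Poisson log link with child-clustered variance, about 5,000 trials per scenario. Simulation B: about 1.7 lesions per child, about 2,300-2,500 usable trials per scenario.

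| Trigger | Setting | Rule selects something | Error under rule | Unadjusted | Depth prespecified |
|---|---|---|---|---|---|
| Any difference | A, 10/arm, 35% progression | 47% | 3.2% | 2.1% | 2.5% |
| Any difference | A, 10/arm, 25% | 61% | 2.6% | not given | 0.9% |
| Any difference | B, 10/arm, 50 / 30 / 20% | 51 / 73 / 83% | 3.7 / 4.0 / 4.9% | not given | not given |
| Any difference | A, 20/arm | 10% | 2.5% | not given | not given |
| p<0.05 screen | A, 10/arm, 35% | 11% | 2.6% | 2.4% | 2.3% |
| p<0.05 screen | B, 10/arm, 50 / 30 / 20% | 11 / 15 / 16% | 2.7 / 1.1 / 1.2% | not given | not given |

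Monte Carlo standard error near 2.5% is √(0.025 × 0.975 / 5,000) = 0.2 points for A and √(0.025 × 0.975 / 2,400) = 0.3 points for B.

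A simpler simulation (C: two arms, continuous child-level outcome, 12 or 20 per arm, six baseline variables, baseline-outcome correlation 0.3-0.7) gave 1.5-2.8% under the rule and 2.2-2.6% with baseline prespecified.

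**5. How often the rule finds baseline depth.** In A (10/arm, 35%): 17% of trials if any difference counts, 3% with the screen. In C: about 14-59% and about 3-6%.

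**6. What prespecification gains.**

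- Count model (A; assumed 50% control progression, rate ratio 0.35, 10/arm): power 34.7% with depth prespecified, 32.9% under the rule, 32.7% unadjusted. The gain over no adjustment is 34.7 − 32.7 = 2.0 points.
- Continuous model (C; 12/arm, effect 1 SD). With the screen: 50-53% under the rule, 54-80% prespecified. If any difference counts: 57-73% and 55-82%. At correlation 0.3 the unscreened rule is not worse (56.8% against 54.9%). C treats the child as the unit, so these levels are not comparable with the plan's 80%.
- Formula: if the SD of 0.2 is that of the change score and the variance is equal at both visits (assumptions), baseline adjustment multiplies the variance by (1 + ρ)/2, where ρ is the correlation between baseline and 12 months. For ρ = 0.3, 0.5, 0.7 and 0.9, the 11.7 children per arm become 7.6, 8.8, 9.9 and 11.1.

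**The case against.** Several points count against a stronger reading.

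- **The odds ratio may be a slip.** Changing one term lets the rule run on the Poisson ratio, as the simulations do. That stands, but the missing threshold, the unnamed contrast and the dependence on the treatment estimate all remain.
- **A reader might infer that the trial's type I error is inflated.** The documents do not support that as a general statement. Inflation appears only if any difference triggers the rule at about 10 per arm. With a significance screen, or with 20 per arm, it is absent or immaterial. The text does not say which reading is meant.
- **A reader might infer that the primary p-value depends on the data.** The chi-squared test comes first and has no covariates, and the plan never calls the GEE the primary model. Nor does it say that an adjusted GEE replaces the unadjusted one. The point is therefore confined to the GEE.
- **A reader might infer that baseline depth is excluded.** It is not; as a clinical variable it can enter through the rule. It is simply not guaranteed.
- **The precision gain is assumed.** No section says how strongly baseline depth predicts change, and in the count model the gain is small for a study described as small and preliminary.

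**Conclusion.** The point holds for the GEE. As written, the rule has no threshold, no named contrast and an effect measure the model does not estimate. Read charitably, it still chooses the model by its effect on the treatment estimate and brings in baseline ICCMS category only by chance.

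The consequence is modest and conditional. Type I error is about 2.6-4.9% against 2.5% if any difference triggers the rule at about 10 children per arm, and about 1.1-2.7% with a p<0.05 screen. The gain from prespecifying baseline category is about 2 points of power in the count model and larger in a continuous one. These figures rest on assumed progression rates, prognostic strength and numbers retained. The defects in the wording rest on the text alone. The rule should be changed, but it does not invalidate the trial.

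**What to change.** In section 13.0:

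1. Delete the imbalance and 15% odds-ratio rule. If it is kept, confine it to an analysis labelled exploratory, with the threshold, contrast and effect scale stated.
2. Prespecify baseline ICCMS category as a fixed covariate in the GEE at 6 and 12 months, whatever the observed balance, with the unadjusted GEE as a sensitivity analysis. State one coding of categories 1, 2 and 3, linear or categorical. Section 3.1 divides category 2 at the dentin-enamel junction, while section 5.1.2 and Appendix I do not, so say that three levels are used.
3. Report the effect on the scale the fitted model estimates: a rate or mean ratio for the log link, not an odds ratio or a mean difference.
4. Define the GEE outcome so that the chosen family can take it. A change score that includes reversal can be negative, which a Poisson or negative binomial family does not allow. Without this step, adding the covariate does not make the model runnable.

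The cost is a few sentences. The covariate is already collected, and it uses one model parameter if linear or two if categorical.

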- 3.3 Follow-Up: Recall examinations and treatment reapplication will be done at 3 months, 6 months, and 12 months after the initial visit in accordance with current American Academy of Pediatric Dentistry (AAPD) guidelines for high caries risks patients⁵. Bitewing radiographs will be taken at 6 months and 12 months. This is in accordance with the "Prescribing Dental Radiographs..." guidelines as approved by the AAPD²⁰, which state that bitewing radiographs in high risk children with dental caries are recommended every 6-12 months.
- 3.4 Providers: Residents and Attendings at the Ostrow School of Dentistry at USC, Pediatric Residency Program. All residents and attendings participating in this study will be trained and standardized on how to identify lesions of interest on radiographs, obtain consent, and apply the medications.
- 3.5 Tracking of study participants: We will count the number of participants who:
 - 1. Those who are asked to participate
 - 2. Those who consent
 - 3. Those who drop out before randomization/after randomization
 - 4. Those who withdraw by their own choice for various reasons
 - 5. Those who are lost to follow up

Note: We will only collect and store clinical data for those participants who continue throughout the duration of the project. If a participant decides to drop out of the study at any time, then we will no longer collect data from the medical record during their ongoing clinical care. We will also discard any previous data we have collected on the participants that drop out.

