10.0 CRITERIA FOR EVALUATION AND ENDPOINT DEFINITIONS

The primary outcome is arrest of interproximal caries on a primary molar, as measured by lack of change in ICCMS classification indicating caries progression on radiographic examination, (higher score indicates progression). The outcome will be evaluated at three time points: baseline, 6 months and 12 months. As the treatments cannot be made to appear similar to one another, neither the treating dentist or the patient/parent(s) will be blinded to treatment status. However, evaluation of the outcome will made by comparing time lapse (ie. comparing intial xrays vs. at 6 months vs. at 1 year) bitewing radiographs and visualizing if the carious lesion has remineralized, arrested, or progressed

11.0 SPECIAL INSTRUCTIONS:

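### At the reported ~48% loss the plan triggers no sensitivity analysis for missing 12-month outcomes, and nothing in it varies the assumption about the children lost

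*Combined protocol and SAP*

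**What the plan says.** The missing-data plan in section 13.0 has three steps.

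1. For missing outcomes or covariates, "we will consider multiple imputation methods if the amount of missing data is <10" per cent.
2. To judge the effect of missing data, "we will compare those with missing data to those not missing data with respect to demographic and clinical variables to assess comparability".
3. Only if imputation is used, "a sensitivity analysis will be conducted excluding those for whom data was imputed to assess the impact of imputation".

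Four other places bear on this:

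- Section 13.1 calls the primary analysis intent-to-treat and says that "10% loss to follow up has increased dramatically to ~48" per cent.
- The note to section 3.5 limits stored clinical data to participants who stay to the end, and adds: "We will also discard any previous data we have collected on the participants that drop out".
- Section 5.3.2: "Any tooth which has progression of caries beyond ICCMS Category 3 will be withdrawn from the study".
- Section 10.0 says that "neither the treating dentist or the patient/parent(s) will be blinded to treatment status".

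No delta-adjusted, tipping-point or worst-case analysis appears anywhere.

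**The concern.** Step 3 depends on step 1, and step 1 does not apply at the loss the trial reports. The 12-month comparison would then rest on about half of the randomised children, with the implicit assumption that the other half did equally well relative to their arm. Step 2 looks only at recorded characteristics. It can suggest that the lost children are a different kind of child, but it cannot show how their lesions fared.

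If step 3 did run, it would set an imputed result beside a complete-case result. Standard imputation may use more information than the complete-case model, such as a 6-month score. Neither analysis, however, allows lost lesions to do worse or better than the observed data predict. The plan itself describes the re-run as a check on imputation, which is a different question from whether loss is informative.

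Families and dentists know the treatment, so return could depend on arm and perceived benefit. The documents do not show that it does, which is why the assumption should be varied openly. At stake is whether a positive or null 12-month result reflects treatment or who came back.

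**Working it through.** **Which steps apply at 48% loss.** With 60 children, the 10% limit is 0.10 × 60 = 6 children. Loss of 48% is 0.48 × 60 = 28.8, about 29. Step 1 is not met, so step 3 is not met either.

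**Inputs (section 13.0, including Power Analysis).** 20 children per arm; 2 lesions per child; difference 0.2; SD 0.2; ICC 0.125 (mean of 0.0 to 0.25); cluster-size variation 0.65, read as a coefficient of variation; two-sided alpha 0.025; power 80%.

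**Reproducing the plan's figure.**

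- Lesions per arm before clustering: 2 × (0.2/0.2)² × (2.2414 + 0.8416)² = 19.01.
- Design effect: 1 + ((0.65² + 1) × 2 − 1) × 0.125 = 1.231.
- Lesions per arm: 19.01 × 1.231 = 23.4, or 11.7 children. This matches the stated 11-12 per group.

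**Precision after loss** (assuming 48% in each arm at 12 months).

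- Retained per arm: 20 × 0.52 = 10.4 children, 20.8 lesions. Lost: 40 × 0.48 = 19.2 lesions.
- SE = √(2 × 0.04 × 1.231 / 20.8) = 0.069.
- Smallest significant difference: 2.2414 × 0.0688 = 0.154 (normal), or about 0.168 with t on about 19 df.

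**Tipping point.** Suppose lost Super Floss lesions did worse than retained ones by δ categories on average, and lost comparator lesions did the same as retained ones. The all-randomised difference is then the observed difference minus 0.48δ. Holding the SE fixed, significance goes at δ = (observed − critical)/0.48. Multiplying by 19.2 gives the number of lost lesions one category worse.

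| Observed difference | Critical value | δ that loses significance | Lesions of about 19 |
|---|---|---|---|
| 0.2 | 0.154 (normal) | 0.046/0.48 = 0.095 | 1.8 |
| 0.2 | 0.168 (t) | 0.032/0.48 = 0.067 | 1.3 |
| 0.3 | 0.154 (normal) | 0.146/0.48 = 0.30 | about 6 |
| 0.4 | 0.154 (normal) | 0.246/0.48 = 0.51 | about 10 |

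The whole of a 0.2 effect goes at δ = 0.2/0.48 = 0.42, or 8 lesions. At 10% loss that would take 0.2/0.10 = 2.0 categories.

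**Across the plan's ICC range** (observed 0.2, normal). At ICC 0 the SE is √(0.08/20.8) = 0.062, the critical value 0.139 and δ = 0.061/0.48 = 0.127 (2.4 lesions). At ICC 0.25 the design effect is 1.461, the SE 0.075, the critical value 0.168 and δ = 0.032/0.48 = 0.067 (1.3 lesions).

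**The reverse case: no true effect.** If the lost-versus-retained gap differs between arms by g, completers show a spurious difference of 0.48g. For g of 0.1, 0.2 and 0.42 this is 0.05, 0.10 and 0.20. With SE 0.0688, the chance of a significant result, 1 − Φ(2.2414 − bias/SE) + Φ(−2.2414 − bias/SE), rises from 2.5% to about 7%, 22% and 75%.

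**The case against.** **The re-run cannot mislead if it is never run.** This stands. A reader might infer that a result could be called robust because the imputed and complete-case analyses agree. At 48% loss the plan produces no such pair. The defect is that nothing is triggered, and the re-run's inability to test informative loss is secondary.

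**The plan does compare children with and without missing data.** It does, so it would be too strong to say that informative loss is bound to go unnoticed. The comparison might reveal a difference in recorded variables. It still cannot reach the missing scores, and the discard rule in section 3.5 may remove the records it needs. Section 3.5 counts drop-outs and those lost to follow-up separately, so how far the rule reaches is unclear.

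**The 1-to-2-lesion figure reflects low power.** Partly true. At 10.4 children per arm, power for 0.2 is about 75%, so an observed 0.2 sits close to the threshold. The table shows that larger observed differences are less fragile.

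**The calculation is not the planned analysis.** True. It compares means, whereas the plan names a cluster-adjusted chi-squared test and a Poisson or negative binomial GEE. It shows scale only. For the same reason, fractional shifts such as 0.1 category would not fit the planned tests, so the fix uses whole categories.

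**Arm-dependent return is conjecture, and this is a small pilot.** All arms share the visit schedule and receive varnish, and the outcome is radiographic. The documents do not show that loss was informative, differed by arm, or was 48% specifically at 12 months. Equally, nothing in them excludes this, and the remedy is cheap for a pilot.

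**Conclusion.** The concern holds in this form: at the reported loss the plan contains no sensitivity analysis for missing outcomes. What is left is a completer analysis plus a comparison that cannot see the missing scores. The conditional re-run would not fill the gap if it were triggered.

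The loss is large enough for modest departures to matter. At an observed difference of 0.2, a shift of 0.07 to 0.10 category in one arm removes significance, and 0.42 removes the effect. At an observed 0.3 the shift needed is about 0.3 category.

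These figures assume equal 48% loss per arm at 12 months, the plan's SD and mean ICC, 0.65 read as a coefficient of variation, a mean-difference approximation, and comparator losses that fare like those retained. They ignore the extra variance from imputation, which would make the result more fragile. The documents give no outcomes for lost children, so they support no claim that the trial's result is biased. They support only that the plan could not tell. A change should be made; it is not a fatal flaw.

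**What to change.** In section 13.0, replace the conditional re-run with a tipping-point analysis of the 12-month comparison, run whatever the amount of missing data:

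1. Count teeth withdrawn under section 5.3.2 for progression beyond category 3 as observed progression. They are not missing, and must not be shifted from a no-change starting point.
2. For the other lesions without a 12-month score, start from a missing-at-random imputation.
3. Make an increasing number of these lesions one ICCMS category worse, in the Super Floss arm alone and then in each comparator alone. Whole categories keep the planned chi-squared test and GEE usable.
4. Report the number of lesions, and the equivalent mean shift, at which the conclusion changes.
5. Keep the complete-case result as description.

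Reconcile the discard rule in section 3.5 with intent-to-treat so that, as far as consent allows, the arm, lesion count, baseline score and any 6-month score of lost children are kept. Without these the analysis may not be feasible.

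The cost is a wording change in sections 3.5 and 13.0 and a little extra analysis, with no new visits or radiographs. The downside is a report that shows how fragile the conclusion is.
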